## **2.2 Background**

Pembrolizumab is a potent humanized IgG4 monoclonal antibody with high specificity of binding to the PD-1 receptor, thus inhibiting its interaction with PD-L1 and PD-L2. Based on preclinical in vitro data, pembrolizumab has high affinity and potent receptor blocking activity for PD-1. Pembrolizumab has an acceptable preclinical safety profile and is in clinical development as an IV immunotherapy for advanced malignancies. KEYTRUDA® (pembrolizumab) is indicated for the treatment of patients across a number of indications. Refer to IB and approved product labeling for specific indications and detailed background information on pembrolizumab.

### **2.2.1 Pharmaceutical and Therapeutic Background**

The importance of intact immune surveillance function in controlling outgrowth of neoplastic transformations has been known for decades [Disis, M. L. 2010]. Accumulating evidence

shows a correlation between tumor-infiltrating lymphocytes in cancer tissue and favorable prognosis in various malignancies. In particular, the presence of cluster of differentiation 8+ (CD8+) T-cells and the ratio of CD8+ effector T-cells/FoxP3+ regulatory T-cells (T-regs) correlates with improved prognosis and long-term survival in solid malignancies, such as ovarian, colorectal, and pancreatic cancer; hepatocellular carcinoma; malignant melanoma; and renal cell carcinoma. Tumor-infiltrating lymphocytes can be expanded *ex vivo* and reinfused, inducing durable objective tumor responses in cancers such as melanoma [Dudley, M. E., et al 2005] [Hunder, N. N., et al 2008].

The PD-1 receptor-ligand interaction is a major pathway hijacked by tumors to suppress immune control. The normal function of PD-1, expressed on the cell surface of activated T-cells under healthy conditions, is to down-modulate unwanted or excessive immune responses, including autoimmune reactions. PD-1 (encoded by the gene *Pdcd1*) is an Ig superfamily member related to CD28 and cytotoxic T-lymphocyte-associated protein 4 (CTLA-4) that has been shown to negatively regulate antigen receptor signaling upon engagement of its ligands (PD L1 and/or PD-L2) [Greenwald, R. J., et al 2005] [Okazaki, T., et al 2001].

The structure of murine PD-1 has been resolved [Zhang, X., et al 2004]. PD-1 and its family members are type-I transmembrane glycoproteins containing an Ig-variable-type domain responsible for ligand binding and a cytoplasmic tail responsible for the binding of signaling molecules. The cytoplasmic tail of PD-1 contains 2 tyrosine-based signaling motifs, an immunoreceptor tyrosine-based inhibition motif, and an immunoreceptor tyrosine-based switch motif. Following T-cell stimulation, PD-1 recruits the tyrosine phosphatases, SHP-1 and SHP-2, to the immunoreceptor tyrosine-based switch motif within its cytoplasmic tail, leading to the dephosphorylation of effector molecules such as CD3 zeta (CD3 $\zeta$ ), protein kinase C-theta (PKC $\theta$ ), and zeta-chain-associated protein kinase (ZAP70), which are involved in the CD3 T-cell signaling cascade [Okazaki, T., et al 2001] [Chemnitz, J. M., et al 2004] [Sheppard, K-A, et al 2004] [Riley, J. L. 2009]. The mechanism by which PD-1 down-modulates T-cell responses is similar to, but distinct from, that of CTLA-4, because both molecules regulate an overlapping set of signaling proteins [Parry, R. V., et al 2005] [Francisco, L. M., et al 2010].

As a consequence, the PD-1/PD-L1 pathway is an attractive target for therapeutic intervention in patients with melanoma.

### **2.2.2 Preclinical and Clinical Studies**

KEYNOTE protocols 001, 002, and 006 have led to the approval of pembrolizumab for the treatment of unresectable or metastatic melanoma in both pretreated and untreated patients. As noted above, clinical studies such as S1404/KN053, EORTC1325/KN054, CheckMate 238, and COMBI-AD are currently exploring the role of adjuvant therapy in Stage III and Stage IV resected melanoma, trying to improve RFS, DMFS, and OS for patients by providing therapy earlier when patients have been deemed free from disease by surgical resection. Benefits of adjuvant therapy have been reported in 3 of these studies so far.

KN051 is currently investigating the safety of pembrolizumab in the pediatric population and has established safe dosing guidelines. Data are currently not available on efficacy of pembrolizumab in advanced pediatric melanoma but this drug has shown efficacy in other

pediatric cancers and is currently approved for treatment of classical Hodgkin lymphoma and microsatellite instability-high tumors [Georger, B., et al 2017].

Refer to the IB and approved product labeling for more details on preclinical and clinical studies of pembrolizumab.

### **2.2.3 Ongoing Clinical Studies**

Clinical development of pembrolizumab is ongoing in a number of advanced solid tumor indications, including advanced melanoma, NSCLC, bladder cancer, head and neck squamous cell carcinoma, other solid tumors, and hematologic malignancies, such as HL.

For study details please refer to the IB.

### **2.3 Benefit/Risk Assessment**

It cannot be guaranteed that participants in clinical studies will directly benefit from treatment during participation, as clinical studies are designed to provide information about the safety and effectiveness of an investigational medicine.

Pembrolizumab has shown activity in adult patients with melanoma, NSCLC, cHL, and head and neck cancer and may have similar effects in pediatric patients. Pembrolizumab has been approved in the United States for the treatment of unresectable or metastatic melanoma in adults and is currently under study in the pediatric population. Recent results from EORTC1325/KN054 show adult patients with Stage III melanoma who receive postresection therapy with pembrolizumab have a significantly longer recurrence-free survival than placebo) making study of adjuvant pembrolizumab in the high-risk Stage II population to improve RFS, DMFS, and OS a natural choice in the adult population (internal Merck data). Some high-risk Stage II patients have MSS rates similar to Stage III patients.

Based on current evidence, no difference in mechanism of action and activity are expected in melanoma between children and adults or between the adjuvant and relapsed/refractory settings. Thus, pembrolizumab has the potential to provide therapeutic benefit to adult and pediatric patients with newly diagnosed and resected high-risk Stage II melanoma. In addition, based on clinical data accrued to date, the safety profile of pembrolizumab in pediatric patients was similar to that seen in adults; therefore, pembrolizumab has the potential to offer children adjuvant therapy for melanoma that is expected to be well tolerated and expected to lead to decreased risk of recurrence, improved DMFS, and OS.

Pembrolizumab appears generally well tolerated at all doses and schedules evaluated to date. These considerations support a favorable benefit-risk assessment for the study of adjuvant pembrolizumab in adult and pediatric participants with high-risk Stage II melanoma.

Additional details regarding specific benefits and risks for participants participating in this clinical study may be found in the accompanying IB and Informed Consent documents.

### 3. Objectives/Hypotheses and Endpoints

In participants 12 years of age and older with surgically resected High-Risk Stage II melanoma:

Objective/Hypothesis	Endpoint
Primary	

 
To compare Recurrence-free Survival (RFS) between treatment arms. Hypothesis (H1): Pembrolizumab is superior to placebo with respect to RFS as assessed by the site investigator.
 
	
 
RFS: time from randomization to (1) any recurrence (local or regional [including invasive ipsilateral tumor and invasive loco-regional tumor], or distant) as assessed by the investigator, or (2) death due to any cause (both cancer and noncancer causes of death)
 

Secondary	

 
Objective: To compare DMFS between treatment arms. Hypothesis (H2): Pembrolizumab is superior to placebo with respect to DMFS as assessed by the site investigator.
 
	
 
DMFS: The time from randomization to appearance of a distant metastasis as assessed by the investigator. A distant metastasis refers to cancer that has spread from the original (primary) tumor to distant organs or distant lymph nodes.
 

 
Objective: To compare OS between treatment arms. Hypothesis (H3): Pembrolizumab is superior to placebo with respect to OS.
 
	
 
OS: The time from randomization to death due to any cause.
 

 
Objective: To assess the safety and tolerability of pembrolizumab compared to placebo in the proportion of AEs.
 
	
 
AEs.
 
Discontinuation of study treatment due to AEs.
 

Tertiary/Exploratory	

 
Objective: To compare average change from baseline during the adjuvant treatment period (up to 21 days after last administration) in global quality of life between the 2 treatment arms using the European Organization for Research and Treatment of Cancer Quality of Life Questionnaire (EORTC QLQ-C30) global health status/QoL scale
 
	
 
EORTC QLQ-C30 global health status/QoL scale.
 

Objective/Hypothesis	Endpoint

 
Objective: To compare average change from baseline after the adjuvant period (from 21 days after last administration) in global quality of life between the 2 treatment arms using the EORTC QLQ-C30 global health status/QoL scale
 
	
 
EORTC QLQ-C30 global health status/QoL scale.
 

 
Objective: To characterize health utilities using the EuroQoL-5 Dimension Questionnaire (EQ-5D-5L) healthy utility scores.
 
	
 
EQ-5D-5L health utility score.
 

 
Objective: to compare the time to subsequent therapy (TTST) between treatment arms
 
	
 
TTST: The time from randomization to the date of first subsequent therapy (eg, surgery, radiation therapy, antineoplastic therapy) or death (whatever the cause), whichever occurs first.
 

 
Objective: to compare Progression/recurrence-free Survival 2 (PRFS2) between treatment arms
 
	
 
PRFS2: Time from randomization to the earliest of the following: (1) date of 1st disease progression per RECIST 1.1 beyond the initial unresectable disease recurrence; (2) date of 2nd recurrence in patients without evidence of disease after surgery of a resectable 1st recurrence; (3) death.
 

 
Objective: To identify molecular (genomic, metabolic, and/or proteomic) biomarkers that may be indicative of clinical response/resistance, safety, pharmacodynamic activity, and/or the mechanism of action of pembrolizumab.
 
	
 
Germline genetic variation, genetic deoxyribonucleic acid (DNA) mutations from tumor, tumor and blood RNA variation, proteomics and immunohistochemistry (IHC), and other biomarkers.
 

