### **6.7 Part 2 – Crossover or Rechallenge Treatment After Recurrence**

The primary goal of the overall study is to compare RFS of pembrolizumab versus placebo, while ensuring access to pembrolizumab for all participants entering the study by allowing crossover/rechallenge after recurrence.

All participants will be unblinded at recurrence (Section 8.1.11) after Sponsor consultation and approval. The site should ensure data for disease recurrence is entered in the database prior to unblinding. Additionally, any AEs and/or SAEs should be reported and causality attributed in the database prior to unblinding. Participants will be encouraged to undergo full resection of the new lesion(s) if they experience local recurrence or have a biopsy if they experience unresectable or metastatic disease. Lymph node dissection should be undertaken per the recommendations of treating physician and surgeon.

For participants who decide to go on to Part 2 and otherwise meet criteria for crossover or rechallenge, resection or biopsy of unresectable or metastatic disease will be mandatory to confirm diagnosis. If biopsy is clinically contraindicated investigators should seek Sponsor review to start participant on Part 2 therapy. Participants should start Part 2 therapy within 4 weeks of recurrence. If participant requires longer time from surgical resection (eg, for recovery from surgery), Sponsor may be consulted to allow additional time before start of Part 2 therapy.

All participants who complete Part 1 study treatment with pembrolizumab or received placebo will be eligible for additional cycles of pembrolizumab if they meet Part 2 enrollment criteria listed below. Rechallenge/crossover is optional and is at the discretion of the Investigator upon notification of the Sponsor.

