Participants assigned in the Part 1 initial treatment phase to the placebo arm who experience recurrence at any point during Part 1 therapy and follow-up and meet all crossover criteria will be offered crossover to pembrolizumab per dosing criteria in Section 4.3. Participants on the pembrolizumab arm during the initial phase of treatment who are greater than 6 months from last dose of pembrolizumab treatment and who experience a recurrence will be offered rechallenge with pembrolizumab per dosing criteria outlined in Section 4.3. Participants who have local recurrence, including local metastatic lymph nodes or distant metastases that are surgically resected may receive up to 17 cycles of therapy with pembrolizumab and participants with an unresectable local (regional metastatic lymph nodes, in-transit, satellite, and/or microsatellite metastases) or an unresectable distant recurrence may receive up to 35 cycles of therapy with pembrolizumab per Section 1.3.2.

All participants should have screening imaging within 28 days prior to C1D1 in Part 2 Crossover/Rechallenge phase. The Part 1 EOT scan can be used as baseline for Part 2 if done within 4 weeks of 1st dose in Part 2. Participants who have had surgical resection of lesion

captured on imaging must have a scan after surgery or radiation is complete to establish baseline imaging within 4 weeks prior to start of Part 2 therapy. Brain MRI must be obtained within 4 weeks prior to start of Part 2 treatment, unless contradicted; then CT may be acquired.

Disease recurrence/progression is confirmed by investigator (radiographically and/or by exam with subsequent biopsy) and RECIST 1.1/iRECIST will be used to identify disease progression in participants with metastatic/unresectable disease identified at the start of Part 2 therapy. Local recurrence should be documented with photo image.

Radiotherapy (palliative or adjuvant) is allowed prior to Part 2 (eg, post lymph node dissection radiotherapy when indicated). Radiotherapy has to be completed prior to first dose and complete wound healing is required prior to first dose. Radiotherapy is allowed during treatment in Part 2 as palliative therapy (treatment of pain, impending fracture, etc.) in participants with unresectable recurrence or metastatic disease. If surgery or radiotherapy other than described above is indicated while on Part 2 therapy Sponsor must be consulted.

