All eligibility criteria from Part 1 Sections 5.1 and 5.2 remain valid and must be reconfirmed prior to enrollment into Part 2 of the study with the EXCEPTION of:

- Inclusion Criteria 2, 3, 4 and 5
- Exclusion Criteria 5, 6 and 11

Participants must also meet the following requirements for entry into Part 2:

- Participant must have experienced an investigator determined/confirmed disease recurrence radiographically and/or by exam with subsequent biopsy. Local recurrence must be documented with photo image. Participants will only be eligible for Part 2 treatment after the first recurrence. If a participant experiences a second recurrence, they will not be eligible for Part 2. Participants who are less than 6 months from their last Part 1 pembrolizumab dose at the time of recurrence are not eligible for Part 2 treatment.

Note: Cutaneous lesions and other superficial lesions detectable only by physical exam must be categorized as nontarget lesions for Part 2 of the study.

- No new anticancer treatment was administered after the last dose of Part 1 study treatment.
- Participant is continuing from Part 1 and has completed 17 cycles of pembrolizumab or any number of cycles with placebo with no delays in treatment  $\geq 12$  weeks. If a  $\geq 12$ -week treatment delay has occurred, Sponsor approval must be obtained before moving into Part 2 of the study.

Note: For any participant who is not able to complete the required 17 cycles of pembrolizumab or have  $\geq 12$ -week treatment delay on placebo arm, a notification to the Sponsor is required to determine if it would impact their eligibility for entry into Part 2.

- Surgical resection or biopsy of unresectable or metastatic disease completed within 4 weeks of first dose.

- Full resection of lesions or biopsy of unresectable or metastatic disease confirmed by site pathologist to be melanoma.

Note: If biopsy is clinically contraindicated, investigators should seek Sponsor review and approval to start participant on Part 2 therapy.

If participant is identified to have a thoracic lesion or lymph node suspicious for a recurrence (especially if solitary lesion), it is encouraged that a biopsy be performed to confirm metastatic melanoma versus another lung primary malignancy versus a nonmalignant lung disease (eg, sarcoidosis).

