3.4.1.3 Tertiary/Exploratory Efficacy Endpoints

Time to Subsequent Therapy (TTST)

Time to subsequent therapy is defined as time from randomization to the date of first subsequent therapy (eg, surgery, radiation therapy, antineoplastic therapy) or death (whatever the cause) whichever occurs first.

Progression-free survival 2 (PRFS2)

Progression/recurrence-free Survival 2 is defined as the time between the date of randomization and the earliest of the following:

- date of 1st disease progression per RECIST1.1 beyond the initial unresectable disease recurrence (unresectable local-regional disease recurrence or unresectable distant metastatic disease recurrence);
- date of 2nd recurrence in Participants without evidence of disease after surgery of a resectable 1st recurrence (resectable local regional recurrences or resectable distant metastatic disease recurrence);
- date of death.

3.4.1.4 Exploratory Endpoints Associated with Protocol Part 2

Progression-Free Survival

Progression-free survival (PFS) is defined as the time from the date of 1st dose in Part 2 to the first documented disease progression or death due to any cause, whichever occurs first.

The following analyses will be done for Part 2.

- PFS per RECIST 1.1 assessed by investigators
- PFS per iRECIST assessed by investigators.

Objective response rate

Objective response rate (ORR) is defined as the proportion of the participants in the analysis population who have a confirmed complete response (CR) or partial response (PR).

The following analyses will be done for Part 2.

- ORR per RECIST 1.1 assessed by investigators
- ORR per iRECIST assessed by investigators.

Duration of Overall Response (DOR)

For participants who demonstrated CR or PR, response duration is defined as the time from first documented evidence of CR or PR until disease progression or death due to any cause, whichever occurs first.

The following analyses will be done for Part 2.

- DOR per RECIST 1.1 assessed by investigators
- DOR per iRECIST assessed by investigators.

Overall Survival (OS)

For Part 2, overall survival is defined as the time from the date of 1st dose in Part 2 to death due to any cause.

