3.6.1.5 Progression-free survival 2 (PRFS2)

The non-parametric Kaplan-Meier method will be used to estimate the distribution for PRFS2. 95% CIs for the median and point estimates at various follow-up times from randomization date will be calculated. Participants who remain alive and whose disease has not recurred, or disease has recurred, but subsequent disease progression or recurrence has not occurred, will be censored on the date of last disease assessments.

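### PRFS2 has no non-death event for a resectable first recurrence that is not resected or not cleared by surgery, and the censoring rule does not cover its progression

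*Protocol*

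**What the plan says.** Protocol Section 3 lists three PRFS2 events, and the earliest counts:

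- the first "disease progression per RECIST 1.1 beyond the initial unresectable disease recurrence";
- a second "recurrence in patients without evidence of disease after surgery of a resectable" first recurrence;
- death.

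Protocol Section 9.4.1.3 and SAP Section 3.4.1.3 repeat the list. The SAP wording of the second event is "date of 2nd recurrence in Participants without evidence of disease after surgery of a resectable 1st recurrence".

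SAP Section 3.6.1.5 sets the censoring. Living participants with no recurrence are censored, and so are those whose "disease has recurred, but subsequent disease progression or recurrence has not occurred, will be censored on the date of last disease assessments". That sentence has no condition on resectability or surgery.

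On management at first recurrence, Protocol Section 6.7 says "Participants will be encouraged to undergo full resection of the new lesion(s) if they experience local recurrence". The tissue requirement for entry to Part 2 is "Full resection of lesions or biopsy of unresectable or metastatic disease confirmed by site pathologist to be melanoma". In the same section, RECIST 1.1/iRECIST "will be used to identify disease progression in participants with metastatic/unresectable disease identified at the start of Part 2 therapy".

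SAP Section 3.6.1 keeps following participants for PRFS2 whether or not they enter Part 2.

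**The concern.** The two non-death events depend on how the first recurrence was managed, and together they do not cover every case. One needs the recurrence to be unresectable. The other needs it to be resectable, operated on, and followed by no evidence of disease. A resectable recurrence that is treated without surgery, or that leaves residual disease after surgery, is in neither group.

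Such cases are foreseeable. Resection at local recurrence is encouraged, not required. Metastatic disease may enter Part 2 on biopsy alone. Participants outside Part 2 have no resection requirement.

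If the event list is programmed as written, a living participant in this group stays event-free through a real second progression, and for that person PRFS2 behaves like overall survival. The objective in Protocol Section 3 and SAP Section 3.3.3 is to compare PRFS2 between arms, so each uncounted progression raises the curve of the arm it belongs to.

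**Working it through.** **1. Do the event list and the censoring rule cover every case?** For a participant alive after a first recurrence:

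| State of first recurrence | No further progression | Further progression |
|---|---|---|
| Unresectable | Censored (SAP 3.6.1.5) | Event 1 |
| Resectable, resected, no evidence of disease | Censored | Event 2 |
| Resectable, resected, residual disease | Censored | No event listed; censoring rule does not apply |
| Resectable, not operated on | Censored | No event listed; censoring rule does not apply |

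The last two cells are empty. A programmer could leave the participant at risk until death, censor at the last assessment, or count the progression. Each choice gives a different PRFS2 time, and no text selects one.

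**2. Does other text assign these cases?** The Part 2 rows of the imaging table (Protocol Section 1.3.3) are either no evidence of disease or unresectable disease. Protocol Section 4.1 makes a similar two-way split for Part 2 treatment. A site could therefore class uncleared disease as unresectable, which would bring it under event 1. Neither section refers to PRFS2, and neither reaches participants outside Part 2.

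**3. Can a direction between arms be derived?** The documents give no PRFS2 event count and no resection or clearance rates. First recurrences by arm can be projected from the RFS design inputs (Protocol Section 9.9.1; SAP Section 3.9): control RFS 68% at 60 months with 50% long-term, HR 0.60, 477 per arm, 16 months of enrollment, 4.7% dropout per year.

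- Control survival: S(t) = 0.5 + 0.5·exp(−λt), with λ = −ln[(0.68 − 0.5)/0.5]/60 = 0.01703 per month. Pembrolizumab: S(t)^0.6.
- Dropout: η = −ln(1 − 0.047)/12 = 0.00401 per month.
- Events per arm at month T: 477 × the average, over uniform entry times a from 0 to 16, of ∫ f(t)·exp(−ηt) dt from 0 to T − a, where f is the event density.

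Check against the plan: 127.2 events at month 33 and 178.7 at month 48, against the stated 128 and 179. A Poisson-type cure model gives 132.7 and 182.5.

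By arm at month 48: 109.4 placebo and 69.3 pembrolizumab.

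Protocol Section 6.7 closes Part 2 to pembrolizumab participants who recur less than 6 months after their last dose. With 17 three-week cycles the last dose is at 16 × 21 = 336 days, about month 11, so the bar runs to about month 17. Projected pembrolizumab first events before month 17 are 35.7, or 35.7/69.3 = 52%. The other 33.6 fall later.

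Let g_in and g_out be the shares of first recurrences in the gap inside and outside Part 2. Both are assumptions. Then placebo = 109.4·g_in and pembrolizumab = 33.6·g_in + 35.7·g_out.

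| g_in | g_out | Placebo, n (share) | Pembrolizumab, n (share) |
|---|---|---|---|
| 5% | 5% | 5.5 (5.0%) | 3.5 (5.0%) |
| 5% | 20% | 5.5 (5.0%) | 8.8 (12.7%) |
| 10% | 5% | 10.9 (10.0%) | 5.1 (7.4%) |
| 2% | 30% | 2.2 (2.0%) | 11.4 (16.5%) |

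The counts are equal when g_out/g_in = (109.4 − 33.6)/35.7 = 2.12. The Poisson form gives 2.08, and month 108 gives 2.62. Over g_in 2–10% and g_out 5–30%, placebo runs from 2.2 to 10.9 and pembrolizumab from 2.5 to 14.1. The order of the arms changes within that range.

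The projection treats every RFS event as a recurrence, puts all placebo recurrences and all later pembrolizumab recurrences in Part 2, and ignores early treatment stops, which would move the month-17 cut-off. It tests direction only and does not estimate how many participants are affected.

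**The case against.** The best defence is that the intended rule can be inferred. The protocol divides recurrent disease in Part 2 into cleared and unresectable, so uncleared disease would be handled as unresectable and fall under event 1. The censoring sentence in SAP Section 3.6.1.5 also implies that any subsequent progression or recurrence ends PRFS2. No decision depends on the result: PRFS2 is exploratory, it lies outside the multiplicity strategy, and the SAP plans Kaplan-Meier estimates with no test or hazard ratio.

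The last argument stands and keeps the point small. The first stands in part: some Part 2 cases may be absorbed in practice. But that classification is never tied to PRFS2 and does not extend outside Part 2. It would also be a site judgement made after first recurrence, when treatment may have been unblinded (Protocol Sections 6.7 and 8.1.11). The inference from the censoring text is reasonable, but it conflicts with the event list, and that conflict is what needs resolving.

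A reader might go further and infer that the gap is larger in the pembrolizumab arm and biases PRFS2 in its favour, since early pembrolizumab recurrences are barred from Part 2. The documents do not support this. They give no clearance rates by arm. The encouragement to resect applies to both arms, before any Part 2 decision. Metastatic disease can enter Part 2 on biopsy alone, and placebo participants have the wider access to Part 2, so that route could put more placebo participants in the gap.

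**Conclusion.** The definitional gap is real on the text of both documents. Unless the site classes the disease as unresectable, progression of a resectable first recurrence that was not resected, or was resected with residual disease, is neither a PRFS2 event nor covered by the censoring rule.

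Its size is unknown. The counts above rest on assumed shares, and even then they are ceilings on missed events, because not everyone in the gap will progress by the analysis. Any difference between arms, and its direction, is also unknown; a higher share per recurrence on pembrolizumab is possible only if clearance is poorer outside Part 2, which the documents do not show. The consequence is limited to the interpretation of an exploratory endpoint. The correction is worth making because it is cheap and removes a conflict between the definition and the censoring text.

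**What to change.** In Protocol Sections 3 and 9.4.1.3 and SAP Section 3.4.1.3, widen the first event to: first progression after a first recurrence that is unresectable, not resected, or not rendered free of disease by surgery, assessed per RECIST 1.1 where RECIST assessments exist and otherwise by documented investigator assessment. Keep the second event for participants rendered disease-free by surgery. Every first recurrence then falls under exactly one non-death event, and the list agrees with the censoring text in SAP Section 3.6.1.5. Report by arm the number of participants in the added category.

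The assessment clause is needed because imaging in DMFS and survival follow-up follows local standard of care or the schedule of a new therapy (Protocol Sections 8.11.3.3 and 8.11.3.4).

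The cost is a wording change and a derivation rule, with no new visits or procedures. There is a small downside: some events would rest on investigator assessment with local-standard imaging instead of RECIST 1.1, and disease status in survival follow-up is collected only if available.
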